### 2.2.1 Primary Outcomes

We will examine the effect of condition (DBT-ER, DBT-IE, IP) on (1a) BPD (as measured by the BSL,) and (1b) emotion regulation (as measured by the DERS,). These outcomes were assessed at baseline mid-treatment, post-treatment, and follow-up. We will examine change slopes within each condition and test how these slopes differ.

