## Study Protocol and Data Analytic Plan

### 1. Brief Description of Protocol

#### 1.1 Protocol Overview

The aim of this study is to compare the effects of DBT emotion regulation skills training (DBT-ER), DBT interpersonal effectiveness skills training (DBT-IE), and an evidence-based interpersonal process (IP) support group developed by [name] on emotional functioning and on BPD-related outcomes. These targets will be assessed using innovative laboratory-based assessment methods. This study uses an NIH Phase III randomized clinical trial to parse the link between elements of DBT skills training modules to specific mechanisms of action. Participants are adults with 4+ BPD criteria and recent, recurrent self-injurious behaviors ( $N = 81$ ). The interventions under study are:

- An orientation meeting plus 6-week DBT-ER skills training group,
- An orientation meeting plus 6-week DBT-IE skills training group, and
- An orientation meeting plus 6-week IP support group

Theorized mechanisms and outcomes will be assessed via self-report and laboratory assessment at baseline (week 0-1), mid-treatment (week 3-4), and post-treatment (week 6-7), and follow-up questionnaires will be administered (week 13-14).

Participants were randomized via the Redcap randomization module, stratified by reported emotion regulation difficulties (above/below 106.87,) the lower end of the cutoff in previous research, and gender.

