## 2. Data Analytic Plan

### 2.1 Preliminary Analyses

Preliminary analyses will examine descriptive data to examine distributional properties of each variable. Transformations (e.g., log transformations) will be applied for variables not meeting normality assumptions. Alternative models (e.g., Poisson or negative binomial) will be used for variables that are not sufficiently normalized by these transformations, as appropriate. Extreme outliers will be considered and adjusted if necessary.

We will consider data missingness. If the data are in fact missing not completely at random, we may only include the ITT sample that also completed at least one of the follow-up timepoints. If data are MAR, we will use Full Information Maximum Likelihood Estimation (FIML),

Preliminary analyses will examine the effectiveness of the lab-based manipulations in the paradigms, to check that the hypothesized emotion induction manipulations operated as expected.

Covariates will be considered per analysis. We will consider including covariates that show associations with the dependent variables (DVs) in analyses particularly if they differ across conditions, including demographic variables, baseline measures of the variables of interest ((and BMI and medication in analyses of physiological variables). Given the small sample size, nonsignificant variables in models may be trimmed from final model reporting.

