## 2.2 Primary Analyses

Given that most of these outcomes will be assessed at Weeks 0 (baseline), 3-4, 6-7, and 13-14, for most primary analyses we will use mixed effects models. We plan to evaluate whether the data are appropriate for use of multilevel models which account for the interdependence of multiple repeated measures within individuals, using full maximum likelihood estimation. Consistent with recommended practices, we will consider a series of models to test how to consider time, levels, and which (if any) random effects to include. If such models do not accurately capture the data, we may resort to single-level regressions. In addition, it is important to consider variability in the group clusters, which is a key strength of using multilevel model analyses to model complex change over time. Given the restraints on sample size imposed by the scope of this proposal, we opted to minimize group-level variability across groups and therapists by retaining the same DBT therapists across the DBT-ER and DBT-IE conditions. Likewise, across all control groups, we will retain the same therapists. We will consider whether to model variability at the level of groups. Alpha will be set to .05 for primary pre-specified outcomes without error correction given the small sample size.

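### The primary slope comparison fixes neither the handling of baseline nor the stratification factors; one model named in advance avoids a power loss and, for DERS, a probably conservative test

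*Combined protocol and SAP*

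**What the plan says.** Section 1.1 gives 81 participants in three conditions, with randomisation "stratified by reported emotion regulation difficulties (above/below 106.87") and by gender. The scale behind the 106.87 cut is not named; DERS is assumed here.

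Section 2.2.1 defines the primary comparison for BSL and DERS: "We will examine change slopes within each condition and test how these slopes differ". Section 2.2 describes the outcomes as "assessed at Weeks 0 (baseline), 3-4, 6-7, and 13-14, for most primary analyses we will use mixed effects models", so week 0 is one of the repeated measurements. It leaves the model's form open: "we will consider a series of models to test how to consider time, levels, and which (if any) random effects to include". It also names full maximum likelihood, leaves group-level variability to be considered, and allows single-level regression as a fallback without giving its form.

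On covariates, section 2.1 says: "We will consider including covariates that show associations with the dependent variables (DVs) in analyses", particularly those that differ across conditions. Demographic variables and baseline measures are among the candidates, and "nonsignificant variables in models may be trimmed from final model reporting". Depending on the missingness found, "we may only include the ITT sample that also completed at least one of the follow-up timepoints".

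Section 2.3 mentions sex and emotion dysregulation only as possible moderators. No section requires a stratification factor in the primary model or says how baseline enters it.

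**The concern.** When week 0 is a response with its own mean in each arm, the model spends information estimating baseline differences that randomisation makes zero in expectation. The slope contrast is then less precise than the data allow. For DERS there is a second effect. If the stratifier is the week-0 score, randomisation has already balanced the arms on something correlated with each person's slope. A model that ignores this overstates the standard error.

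Two things are at stake: power in a trial that itself calls its sample small, and the number of primary results the plan permits. Covariates chosen by association with the outcome, trimming by p-value and an open model structure allow several analyses of each outcome, each at an uncorrected .05.

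**Working it through.** **Inputs.** From the documents: N = 81, three conditions, visits at weeks 0, 3-4, 6-7 and 13-14, alpha .05. Assumed: equal allocation (81/3 = 27 per arm), two-sided tests, visits at t = 0, 3.5, 6.5, 13.5, SD 1, an effect of 0.5 SD at week 13.5, linear time, no dropout and no group effect. The plan has no power figure to reproduce.

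**Free versus common baseline.** With n per arm and within-person covariance V, the variance of the slope difference is:

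- free baselines: (2/n) / [t′V⁻¹t − (1′V⁻¹t)²/(1′V⁻¹1)]
- common baseline: (2/n) / (t′V⁻¹t)

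Here Σt = 23.5, Σt² = 236.75 and Σ(t − 5.875)² = 98.69. For constant correlation 0.5:

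- free: (2/27)(0.5)/98.69 = 0.000375; SE over 13.5 weeks = 13.5 × √0.000375 = 0.262
- common: t′V⁻¹t = (236.75 − 0.2 × 552.25)/0.5 = 252.6; (2/27)/252.6 = 0.000293; SE = 0.231

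Power comes from the noncentral t distribution with 81 − 3 = 78 df and noncentrality 0.5/SE:

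| Covariance | SE free | SE common | Variance ratio | Power, free to common |
|---|---|---|---|---|
| constant 0.5 | 0.262 | 0.231 | 0.78 | 47 to 57% |
| constant 0.7 | 0.203 | 0.190 | 0.88 | 68 to 74% |
| decaying, 0.5 per 6.5 weeks | 0.336 | 0.262 | 0.61 | 31 to 47% |

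**Where the gain shrinks.**

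- Therapy groups, assuming three per arm with group-slope variance 5 to 10% of baseline variance: this adds 2 × 0.05/3 = 0.033 to 2 × 0.10/3 = 0.067 to both squared SEs. The gain becomes 1.3 to 4.8 points under constant correlation and 5.5 to 8.7 under decay.
- Random slopes: 3 to 8 points for slope variance 0.1 to 0.4 at week 13.5. It is about 1 point (29 to 30%, normal approximation) when the slope SD is 0.08 per week, a variance of (0.08 × 13.5)² = 1.17.
- Dropout, with 21 of 27 per arm reaching the last wave: 40 to 48%, 59 to 64% and 28 to 40% for the three rows.

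**Stratum terms with free baselines.** A stratum main effect shifts level, not slope. In a random-intercept model with residual variance 0.4, the SE per week is √[(2/27)(0.4)/98.69] = 0.01733 with or without it. Stratum-by-time terms do help for DERS. Simulation (6,000 trials per cell, stratified blocks, cut assumed at the median, individual slopes compared across arms) gave:

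| DERS covariance | Free | + stratum- and gender-by-time | Continuous baseline | Share recovered |
|---|---|---|---|---|
| constant 0.5 | 46.9% | 51.5% | 54.2% | 4.6/7.3 = 63% |
| constant 0.7 | 68.4% | 70.7% | 72.9% | 2.3/4.5 = 51% |
| decaying | 29.5% | 40.2% | 47.1% | 10.7/17.6 = 61% |

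A repeat gave 46 to 50%, 70 to 73% and 29 to 39% for the step from free to stratum-by-time. This share is what one would expect: a median split correlates 0.798 with the score, and 0.798² = 0.64. With a 20/80 split it would be 0.70² = 0.49. Null rejection moved from 2.3 to 4.7% with free baselines to about 5% with these terms. The corresponding free-baseline model was not computed for BSL.

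**Estimation method.** Under the null, a common-baseline model rejected 5.7 to 7.4% with uncorrected full ML. The proposed model with REML and Kenward-Roger df rejected 4.1 to 5.8%.

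**Time coding.** If the effect reaches 0.5 SD at week 6.5 and then holds (constant correlation 0.5), the free-baseline slope implies 0.48 SD at week 13.5 and the common-baseline slope 0.53. If it halves to 0.25 by week 13.5, they imply 0.22 and 0.30.

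**Single-level fallback at one wave.** The variances are 1 (post only), 2(1 − ρ) (change) and 1 − ρ² (baseline-adjusted). For ρ from 0.5 to 0.7, power is 44%, 44 to 65% and 55 to 71% respectively.

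**The case against.** The strongest reply is that the plan does not exclude any of this. Baseline measures are listed as candidate covariates, the model series could end in a baseline-adjusted model, and arm-specific baselines are a permitted reading, not a stated choice. That is correct. The criticism is that the choice is not fixed, not that baseline is ignored.

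A second reply is that no input to the power gain comes from the documents, and the gain can be as small as 1 point. This also stands. It makes pre-specification the firmer argument and power the secondary one.

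Third, a common baseline has its own costs. It relies on the baseline visit preceding allocation, and section 1.1 places baseline at week 0-1 without saying which came first. If allocation itself created a persistent 0.2 SD baseline difference, null rejection would be 6.5 to 10.3% with a common baseline, against 4.3 to 5.3% with free baselines. The two models also estimate different quantities if change is not linear once treatment ends. Both points are conditions on the fix.

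A reader might infer that the planned test is invalid or has an inflated error rate because the stratifiers are left out. The calculations do not support that: with free baselines the test is roughly valid, and for DERS it errs towards too few rejections. A reader might also infer from the past tense in sections 1.1 and 2.2.1 that outcomes had already been examined by arm. The documents do not say so.

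**Conclusion.** The concern holds as a recommended improvement, with medium confidence; it does not invalidate the trial. The plan permits a primary slope test with arm-specific baselines and no stratum-by-time terms. In the base cases that costs about 5 to 16 points of power. The cost falls to about 1 to 5 points with therapy-group effects under constant correlation, or with large random-slope variance. For DERS the test is also conservative, provided the stratifier is week-0 DERS. Stratum- and gender-by-time terms alone would then recover roughly half or more of the gain and bring null rejection back to about 5%; stratum main effects alone recover none.

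Every figure rests on the assumed effect, correlations, equal allocation and linear time. No single power loss can be attributed to this trial.

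**What to change.** Before outcome data are analysed by arm, name one primary model for BSL and DERS and keep its terms whatever their p-values:

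- Include all randomised participants with a baseline, and constrain the baseline mean to be equal across arms.
- Include arm-by-time, gender-by-time and, for BSL, baseline DERS-by-time. Do not use baseline DERS as both response and covariate.
- Use REML with Kenward-Roger degrees of freedom.
- State the time coding, and so which slope difference is being estimated.
- If the baseline assessment followed allocation, keep arm-specific baselines with stratifier-by-time and gender-by-time.
- Require baseline and the stratifiers in any single-level fallback.
- Report other covariate selection or trimming, and the sample limited to those with a follow-up, as sensitivity analyses.
- If data have already been seen by arm, label the choice post hoc.

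The cost is SAP wording, a few degrees of freedom, reliance on baseline preceding allocation, and a check of that timing. No extra participants, visits or measures are needed: the baseline outcomes are already scheduled, and the stratifying score and gender are needed for randomisation.

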#### 1.2 Methods Summary

Self-report measures will be assessed at baseline, mid-treatment (week 3-4), post-treatment (week 6-7), and follow-up (week 13-14). Primary (namely BPD symptoms on the Borderline Symptom List, BSL, emotion dysregulation on the Difficulties in Emotion Regulation Scale, DERS,) and Secondary (DBT skills use on the DBT-WCCL,) self-report p|outcomes are indicated below, although additional measures will also be included. Laboratory-based paradigms will be assessed at baseline, mid-treatment, and post-treatment.

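### Does the plan need to name one primary test for BSL and DERS, and give pairwise and within-condition slopes a formal status?

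*Combined protocol and SAP*

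**What the plan says.** Section 1.2 of the combined protocol and SAP names the primary outcomes, BSL for borderline symptoms ("Primary (namely BPD symptoms on the Borderline Symptom List, BSL") and DERS for emotion dysregulation. Section 2.2.1 opens with the target of inference, the "effect of condition (DBT-ER, DBT-IE, IP) on (1a) BPD" and on DERS, and lists four assessments, from baseline to follow-up. It closes with: "We will examine change slopes within each condition and test how these slopes differ".

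Section 2.2 sets the error rate: "Alpha will be set to .05 for primary pre-specified outcomes without error correction given the small sample size". It plans mixed effects models for most primary analyses and leaves their form to model building: "we will consider a series of models to test how to consider time, levels, and which (if any) random effects to include".

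No section names an omnibus test, a reference arm, a key contrast or the period that the slope covers (to week 6-7 or to week 13-14). None ranks pairwise or within-condition slopes as primary or supportive.

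**The concern.** With three conditions, a test of how slopes differ can be one omnibus condition-by-time test or three pairwise contrasts, and the two can disagree. Over two outcomes the count runs from two tests to six. Adding the six within-condition slopes makes twelve, all at an uncorrected .05. If any of them could be called the primary result, the chance of a false claim would rise well above 5%.

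The within-condition slopes look the most hazardous. They do not compare randomised groups, yet they appear in the Primary Outcomes section. In small arms, three equally effective conditions will often show some significant slopes and some not. A reader could take significance in a DBT arm, with none in the IP arm, as evidence that DBT works better.

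**Working it through.** **Inputs.** From the documents: three arms, two primary outcomes, N = 81 (section 1.1) and alpha .05 uncorrected (section 2.2). Assumed: 27 per arm (81/3; the allocation ratio is not stated), two-sided tests, complete data, one slope per person, no clustering, effects in SD of that slope, and a BSL-DERS correlation of 0 to 0.8. The plan gives no power or sample-size figure to reproduce.

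**1. False positives when the arms do not differ.** For k independent tests the chance of at least one is 1 - 0.95^k. Simulation replaces this where tests are dependent.

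| Reading | k | If independent | Simulated |
|---|---|---|---|
| One condition-by-time test per outcome | 2 | 1 - 0.95^2 = 9.75% | 7.9-9.8% |
| Three pairwise contrasts per outcome | 6 | 1 - 0.95^6 = 26.5% | 18.3-22.9% |
| Pairwise plus within-condition slopes | 12 | 1 - 0.95^12 = 46.0% | 29-34% |

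The last simulated figure uses correlations of 0 to 0.7 and also requires every true slope to be zero.

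**2. Disagreement between the readings.** On one outcome, a pairwise contrast is significant while the overall test is not in 7% of trials with no effect. The figure is 15-17% when the largest arm difference is 0.4-0.6 SD, and 7-12% at 0.8 SD.

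**3. Mixed within-condition slopes when all arms improve equally.** Let p be the power of a one-sample t test with n = 27. The chance that some slopes are significant and others not is 1 - p^3 - (1-p)^3. The chance that at least one DBT arm is significant and IP is not is (1-p)[1 - (1-p)^2]. At 0.4 SD, p = 0.517:

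- mixed pattern: 1 - 0.138 - 0.113 = 74.9%
- DBT but not IP: 0.483 × (1 - 0.234) = 37.0%

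| Common improvement (SD) | p | Mixed | DBT but not IP |
|---|---|---|---|
| 0.3 | 32% | 66% | 37% |
| 0.4 | 52% | 75% | 37% |
| 0.5 | 71% | 62% | 27% |
| 0.6 | 85% | 38% | 15% |
| 0.8 | 98% | 6% | 2% |

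The condition-by-time test rejects in 5% throughout.

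**4. Would fixing the omnibus as primary be a clear gain?** Take one contrast of size d with the third arm midway. The pairwise t test (78 df) has noncentrality d√(27/2). The 2-df F test has noncentrality 27d²/2.

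- d = 0.8: F noncentrality 8.64, power 73.5%, against 82.7% for the pairwise test.
- d = 0.6: F noncentrality 4.86, power 47.6%, against 58.6%.

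The overall test therefore gives up 9 to 11 points for that contrast. Named contrasts avoid this loss but raise the count of primary tests.

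**5. What the wording supports.** Section 2.2.1 speaks of one effect of a three-level condition. It examines slopes within conditions but tests the differences between them. Section 1.1 states the aim as a comparison of the three interventions. Section 2.2.2 follows the same pattern for the secondary outcomes: change over time is modelled, then compared across conditions. All three sections point to the first row of the table in step 1.

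**The case for a change.** The strongest case for acting is that the plan never states the status of these results and that stating it is cheap. A trial described as Phase III, with no multiplicity correction, has more reason than most to say which tests its .05 covers. The sentence in 2.2.1 fits both an omnibus and a pairwise reading, and step 2 shows that they disagree in 7-17% of trials. Nothing expressly bars reporting the pattern in step 3, which occurs in 27-37% of trials at common improvements of 0.3-0.5 SD.

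The silence stands, and so do the numbers. The time window is also unstated, and the degrees of freedom depend on how time enters: 2 if linear, (3-1) × (4-1) = 6 if the four visits are categories.

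The inference from them to a needed change is weaker. The step 3 percentages say how often a pattern appears; they are not an error rate of the planned comparison. To do harm the pattern must be reported as a difference between conditions, although 2.2.1 commits to testing that difference directly. The figures also rest on effect sizes the documents do not give, and fall to 6% and 2% at 0.8 SD. The disagreement in step 2 reflects a genuine choice between two defensible tests, and step 4 shows that neither dominates.

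**Conclusion.** No change is called for. This is missing detail that a competent analyst fills sensibly: one condition-by-time test per outcome, with pairwise differences used to describe it and within-condition slopes as description. Done that way, the error rate is 5% per outcome and 7.9-9.8% over both. Naming the test would leave both figures as they are, because the excess over 5% comes from the uncorrected alpha that section 2.2 adopts openly. The 18-23% rate belongs to the less natural reading, in which any of six contrasts counts as primary. Choosing between an omnibus test and named contrasts is a trade-off for the sponsor.

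The figures assume 27 per arm, complete data, a single slope per person, independent participants and a BSL-DERS correlation of 0 to 0.8. The 5% also presumes that the form of time is not chosen by its effect on the condition result and that any group clustering is handled. Section 2.2 leaves the latter open ("We will consider whether to model variability at the level of groups"). These are separate modelling questions, which labelling the tests in 2.2.1 would not settle.

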### 2.2.2 Secondary Outcomes

We will examine the effect of condition (DBT-ER, DBT-IE, IP) on changes in (2) emotional reactivity and regulation in response to a deliberate emotion regulation paradigm (with Maintain, Decrease, and Neutral instructions) on (2a) self-report on the PANAS negative affect scale, (2b) skin conductance, and (2c) high-frequency heart rate variability. Likewise, we will examine the effect of condition (DBT-ER, DBT-IE, IP) on changes in (3) affect-modulated startle (e.g., eyeblink amplitude assessed via EMG to Neutral vs. Negative [repeated and novel] images with associated probes, corrected for startle-only trials). These outcomes will be assessed repeatedly within each baseline, mid-treatment, and post-treatment laboratory session (no follow-up assessment was conducted for these outcomes). As described above, where appropriate we will leverage the repeated measures nature of these data to increase power, but may collapse across levels of data if appropriate to best model variability (e.g., we may create difference scores for startle outcomes across categories; we may aggregate counts of self-injury or attempts post treatment as a single level outcome rather than modeling change via a latent growth curve model if insufficient fluctuation in these outcomes is found). Mixed effects models will test the change across time in self-reported affect, skin conductance, and heart rate variability in the paradigms over treatment, and will compare these time effects across conditions.

## 2.3 Additional Analyses

Although not included as primary or secondary outcomes, we will also examine the effects of Condition and Time on self-injurious behaviors ( although these have a low base rate and may not be possible to model in a latent growth curve analysis) and interpersonal targets (e.g., interpersonal bias, interpersonal emotion regulation, and interpersonal problem solving). Further, we will consider sex (if adequately powered), emotion dysregulation and interpersonal functioning and diagnosis (especially co-occurring PTSD) as moderators of treatment response. Furthermore, although potentially underpowered, we will also consider whether change in interpersonal or emotional targets predict subsequent changes in BPD symptoms on the BSL (and self-injury, if possible) differentially based on Condition.

